**Prospective surveillance for very early hepatocellular carcinoma
(PRECAR): a study protocol for an observational multicenter cohort
trial**

NCT number: 03588442

Date:2020.4.30

Version: v1.0

Abstract

Background: Approximately 20% patients are diagnosed to hepatocellular carcinoma at early stage, when effective treatments are feasible, and benefit from curative therapeutic approaches, such as hepatic resection and liver transplantation. Biannual ultrasound is recommended for patients with cirrhosis for early diagnosis of hepatocellular carcinoma. However, limited sensitivity and false-positivity call for development of a new surveillance tool with prior accuracy. This study aims to build a biosignature to stratify high risk population for developing hepatocellular carcinoma and to diagnosis hepatocellular carcinomas at very early stage using biological signature.

Methods: This investigator-initiated, multicenter, observational, cohort trial will enroll 5000 patients with liver cirrhosis and 5000 patients with hepatitis B virus infection. Exclusion criteria include human immunodeficiency virus infection, previous diagnosis of active pulmonary tuberculosis, and pregnancy. Patients will be recruited for 1 year and follow-up investigation will be performed biannually for 3 years to collect demographic and clinical characteristics, blood samples, disease status, and outcome data. Development of hepatocellular carcinoma and overall survival are the primary endpoints, which will be contributed to the development of the biosignature for risk stratification for incidence, diagnosis at very early stage, and survival prediction. The secondary endpoints include development of non-hepatocellular carcinoma hepatic malignancy, liver resection rate, postresection survival, and relapse-free survival.

Discussion: The biosignature will be useful in clinical practice by stratifying patients with cirrhosis or hepatitis B virus infection at high risk for development of hepatocellular carcinoma and diagnosing at very early stage.

Trial registration: ClinicalTrials.gov identifier, NCTxx, first received xx, xx 2018.

Key words: liver cancer, diagnosis, early stage, observational cohort trial, biosignature, prediction model

Introduction

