Justification of inclusion criteria for a surveillance program is determined by the risk of HCC life expectancy, and cost-effectiveness.¹² Regarding absence of experimental data, the decision for patient inclusion is based on its efficacy evaluated by heterogeneous designs, indicating that the efficacy of a surveillance program is dependent to incidence of HCC. Accordingly, populations with liver cirrhosis and HBV infection are currently recommended for surveillance.¹³

Ultrasonography and serum tumor markers are the preferred tests for surveillance of HCC based on toleration, availability, non-invasiveness, and sensitivity. Ultrasonography has a reported sensitivity of 60 to 80%, whereas α -fetoprotein was approximately 60% with the most efficient cut-off (10 to 20 ng/mL).^{14,15} Combination of ultrasonography and α -fetoprotein may increase accuracy, but also increases false-positivity and cost. Regarding importance of diagnosis of HCC at early stage, there is an unmet need for a well-made surveillance model to detect early HCC with priority in accuracy and sensitivity; identification of populations at high risk before development of HCC may be ideal if high sensitivity is achieved. In addition, it may prevent up to 6 months of disease progression and improve diagnostic sensitivity, ultimately improving prognosis.

The Prospective Surveillance for Very Early Hepatocellular Carcinoma (PRECAR) trial is designed as an observational multicenter cohort trial to conduct a signature to detect and define very early HCC and individuals at high risk of HCC by analyzing genome sequencing, plasma-

free DNA sequencing, and high-throughput protein expression screening.

Methods and Design

Ethics

The PRECAR trial will be conducted in accordance with the Declaration of Helsinki and current Good Clinical Practice guidelines. The relevant ethics committee approval will be obtained before enrolment of patients. Informed consents will be obtained from all participants before enrollment.

Eligible population

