The inclusion and exclusion criteria for the PRECAR trial are described in Table 1. Briefly, two independent cohorts (cirrhosis cohort and HBV infection cohort) will be recruited for surveillance of HCC. The cirrhosis cohort will be consisted of patients with biopsy diagnosis or distinctive clinical characteristics of cirrhotic liver regardless etiology of cirrhosis. For HBV infection cohort, seropositivity of hepatitis B surface antigen is the basic condition for inclusion.

Overview of trial design

PRECAR is a prospective, observational, multicenter trial surveilling development of HCC in patients with cirrhosis or HBV infection. In PRECAR, the aim will be to recruit a total of 10,000 patients (5000 each for the two cohorts) from a minimum of 10 sites. Follow-up will be carried out for eligible patients for collection of demographic, clinical, and serological characteristics and samples for analyses. For those who developed HCC, hepatic resection will be the standard

of care unless unresectable. Data of interest and schedule for the PRECAR trial are summarized in Table 2.

Outcome measures

The primary endpoints of the PRECAR trial include development of HCC, overall survival (OS), and liver-related disease progression (LDP). Secondary endpoints are development of non-HCC malignant neoplasm, such as intrahepatic cholangiocarcinoma, liver resection rate (LRR), and postoperative overall (POS) and relapse-free survival (PRFS) after development of liver malignant neoplasm.

Outcome definitions

HCC – the time from the date of inclusion to development of HCC.

OS – the time from the date of inclusion to death from any cause.

LDP – the time from the date of inclusion to non-malignancy-associated liver-related disease progression or death, whichever is earlier.

Non-HCC – the time from the date of inclusion to development of non-HCC malignant neoplasm.

LRR – the number of malignancy-developed patients whose tumor is resectable without vascular invasion and extrahepatic metastasis.

POS – the time from the date of liver resection to death from any cause.

PRFS – the time from the date of liver resection to tumor progression in the liver or death, whichever is earlier.

Blood collection for biosignature analysis

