Peripheral blood samples (25 ml) will be collected from all consenting patients at first 3 follow-up (0, 6th, and 12th month), which will be used to develop a biosignature to stratify patients at high risk for development of HCC. After development of a biosignature, 20 ml of peripheral blood samples will be collected from patients at high risk for HCC at 4th to 7th follow-up for modification and validation of the biosignature.

Statistical analysis

All statistical analyses will be performed using R (<http://www.r-project.org/>) or SPSS (Chicago, IL). Cox hazards proportional model and logistic regression will be applied to screen factors for the inclusion in a biosignature. Correlation test will be performed between results of multivariate Cox and logistic regressions, and false-positive factors will be deleted. After screening covariates, receiver operating characteristic (ROC) curves will be constructed to calculate optimum threshold for setting of cut-off value to define high risk for HCC. Independent demographic and clinical prognostic factors may be combined with the biosignature to improve performance sensitivity and specificity. Predictive signatures for cirrhosis cohort and HBV infection cohort will be developed independently. A correction for multiple testing may be applied.

Discussion

The PRECAR trial will identify predictors for development of HCC and diagnosis of very early

HCC by comparing HCC cases arising from cirrhosis or HBV infection with non-HCC developing cases. To the best of our knowledge, no prospective observational cohort trial has been published with intent to develop a biosignature to stratify patients at high risk for HCC. However, a case control study with similar design (miRNA as a diagnostic tool for HCC) is ongoing in South Africa, where HIV is hyper endemic, thus the etiology of HCC is different from the PRECAR.¹⁶ In addition, ideal aim of the PRECAR trial is to successfully stratify patients who have high potential to develop HCC and carry out intensive follow-up to prevent up to 6 months of disease progression, as well as to offer curative therapeutic options at very early stage to improve prognosis.

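### The signature rests on Cox and logistic regression with no stated shrinkage or resampling; if its score comes from those fits after a lenient screen, it will be overfitted and its apparent accuracy too high

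*Combined protocol and SAP*

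**What the plan says.** The last paragraph of the Introduction gives the source of the candidates: genome sequencing, plasma-"free DNA sequencing, and high-throughput protein expression screening". The number of candidates is not given.

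The Statistical analysis section sets out the steps:

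- **Screen:** "Cox hazards proportional model and logistic regression will be applied to screen factors for the inclusion in a biosignature".
- **Filter:** "Correlation test will be performed between results of multivariate Cox and logistic regressions", and factors judged to be false positives are then dropped.
- **Cut-off:** ROC curves then fix the threshold for high risk. Clinical factors may be added, and a multiplicity correction is optional.
- **By cohort:** "Predictive signatures for cirrhosis cohort and HBV infection cohort will be developed independently".

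The section on blood collection says that development samples "will be collected from all consenting patients at first 3 follow-up (0, 6th, and 12th month"). Later samples come only from patients already classed as high risk, and they serve both to modify and to validate the signature.

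The overview of the design plans to "recruit a total of 10,000 patients (5000 each for the two cohorts) from a minimum of 10 sites". No HCC incidence, expected event count, entry rule for the screen, number of markers to be kept or method of weighting is given. Neither shrinkage nor resampling is mentioned.

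**The concern.** A ROC cut-off needs a continuous score, and a score needs weights. The multivariate Cox and logistic fits are the only source of weights that the plan names. When markers are picked because they look strong in a set of patients, and are then given unshrunken coefficients in the same patients, those coefficients are too large on average and some belong to noise.

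Two things are at stake. The AUC, sensitivity and specificity read from the development data would look much better than the signature will perform in new patients. The score may also order patients less well than it could, and that order decides who is called high risk, which is the stated purpose of the study. The later validation does not repair this, because it is restricted to patients whom the signature has already selected and is combined with changing it.

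**Working it through.** **No figure to reproduce.** The 10,000 (5000 + 5000) comes without incidence, events, candidate count or target accuracy. Everything below rests on assumptions.

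**1. Events per cohort.** With 5000 patients, annual HCC incidence r (assumed) and no dropout, events over t years = 5000 × (1 − (1 − r)^t).

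| r per year | 3 years | 1 year |
|---|---|---|
| 0.2% | 30 | 10 |
| 0.5% | 75 | 25 |
| 1% | 149 | 50 |
| 2% | 294 | 100 |
| 3% | 437 | 150 |
| 5% | 713 | 250 |

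The one-year column matters because the development samples end at month 12 and the signature is meant to exist by the month-18 visit.

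**2. Parameters that the data support.** For expected shrinkage S = 0.9, p = n(S − 1) ln(1 − R²/S), with R² assumed to be 15% of its maximum, 1 − [φ^φ(1 − φ)^(1−φ)]², at 3-year risk φ. For φ = 3%, the maximum is 0.236 and R² = 0.0354, so p = 5000 × (−0.1) × ln(1 − 0.0394) = 20. For φ = 1%, 6% and 9%, p is 8, 31 and 39 (rounded down).

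**3. Noise that passes a p<0.05 screen.** With 10 true markers, about 0.05 × 290 = 14.5 null markers pass out of 300 candidates, and 0.05 × 990 = 49.5 out of 1000. The second number exceeds the 20 parameters supported at 150 events (φ = 3%) and the 39 supported at 450 (φ = 9%).

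**4. Simulated overfitting.** Assumed: 5000 patients, independent markers, 10 true (odds ratio 1.35 per SD), p<0.05 screen, then an unpenalised multivariable fit, tested in new patients. Logistic regression stands in for Cox because events are rare.

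| Events | Slope, 300 to 1000 candidates | Apparent vs test AUC, 300 candidates |
|---|---|---|
| 75 | 0.14-0.36 | 0.84 vs 0.63 (gap 0.21) |
| 150 | 0.28-0.57 | 0.81 vs 0.69 (gap 0.12) |
| 450 | 0.52-0.79 | 0.77 vs 0.71 (gap 0.06) |

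A correct slope is 1. A slope of 0.36 means that risk contrasts are overstated 1/0.36 = 2.8-fold on the log scale. Over all settings the AUC gap runs from about 0.05 to about 0.35, largest with 1000 candidates and 75 events.

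**5. Ranking against a cross-validated lasso.** With 300 candidates (about 60 data sets per setting), lasso minus screened fit was −0.002 (SE 0.005) at 75 events, 0.016 (SE 0.001) at 150 and 0.015 (SE 0.001) at 450. With 1000 candidates the gain of lasso or elastic net was about 0.045 at 150 or more events. With a strict screen (p<0.001) there was almost no gain at 450.

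A second simulation used 400 candidates, 5 or 20 true, correlation 0 or 0.5, and only 5 data sets per setting. Mean test AUC, screened fit → lasso:

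| Events | 5 true, r=0 | 5 true, r=0.5 | 20 true, r=0 | 20 true, r=0.5 |
|---|---|---|---|---|
| 20 | 0.598 → 0.567 | 0.578 → 0.516 | 0.528 → 0.532 | 0.597 → 0.525 |
| 75 | 0.673 → 0.710 | 0.687 → 0.707 | 0.618 → 0.585 | 0.638 → 0.609 |
| 150 | 0.683 → 0.731 | 0.706 → 0.742 | 0.673 → 0.681 | 0.685 → 0.693 |
| 450 | 0.718 → 0.742 | 0.717 → 0.739 | 0.721 → 0.727 | 0.716 → 0.729 |

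The gain is positive throughout at 150 and 450 events (0.006 to 0.048). It changes sign at 75, and at 20 lasso is usually worse.

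**6. What drives the ranking gain.** Ridge regression on the same screened markers (500 candidates) changed test AUC by only −0.003 to +0.004. The gain therefore comes from selecting and shrinking jointly, not from shrinking a fixed set.

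**The case against.** The strongest reply is that the plan uses the regressions to screen factors and never says that their coefficients become the weights; a penalised Cox model is still a Cox model. This stands. The weighting method is unstated, so the concern is conditional on the weights coming from these fits. Silence does not exclude a better method, but it does not commit the study to one either.

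A second reply is that the planned output is a ROC cut-off, and rescaling a score uniformly changes neither its ROC curve nor who lies above the threshold. This is right about the slope taken alone. It does not rescue the apparent AUC or the accuracy at the cut-off, for which the plan names no separate data.

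Third, every magnitude is assumed, and the simulations leave out the correlation-and-deletion step and the optional multiplicity correction. That is fair: a strict screen removes most of the ranking loss at about 450 events.

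A reader might also infer three stronger claims, none of which is supported:

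- **That more candidates than events leaves the fits without a unique solution.** The condition is separation or rank deficiency. With about 75 events, unpenalised fits with 80 to 200 independent candidates all converged to finite solutions, as did fits with 160 or 300 candidates at about 150 events.
- **That ranking suffers most in the cohort with fewest events.** At 75 events or fewer no reliable gain from penalisation is shown.
- **That HCC cases will be few.** The document gives no incidence.

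**Conclusion.** The point holds in conditional form. The plan states neither how the score is weighted nor any protection against overfitting. If the score is taken from the named multivariate fits after a lenient screen, overfitting is present at every event count examined, including 450: slopes run from 0.14 to 0.79, and apparent AUC is too high by about 0.05 to 0.35. The ranking loss is smaller and less general: about 0.015 AUC (300 candidates) to 0.045 (1000 candidates) at 150 or more events, not reliably present at 75 or fewer, and largely gone at about 450 events under a strict screen.

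These sizes rest on assumed event counts, candidate numbers, effect sizes and screening threshold, and on logistic rather than Cox fits. They show direction and plausible scale, not this study's actual loss. The case for change is the low cost of the remedy and the size of the optimism, more than the gain in ranking.

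**What to change.** In the Statistical analysis section, replace the sequence of screen, multivariate fit and correlation test as the source of the score. For each cohort:

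- State the expected number of HCC events available for development and the number of candidate markers.
- Derive the score by penalised Cox regression (lasso or elastic net) on time to HCC, choosing the penalty by cross-validation over patients and leaving established clinical factors unpenalised.
- Repeat the whole selection and fitting inside bootstrap or cross-validation, and report optimism-corrected AUC and calibration.
- Keep the ordinary Cox and logistic results as descriptive.

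The cost is SAP wording and computing time. R is already named and has standard packages; no new samples or visits are needed. There are downsides. Coefficients are shrunken (the lasso's own slope was about 1.2 to 1.4, so its risk contrasts are somewhat understated), there is no simple p-value per marker, and selection may be unstable or empty when events are very few. The plan should say in advance what will be done in that last case.

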China has among the highest incidence and mortality of hepatocellular carcinoma (HCC) in the world with increasing trend.^{1,2} Prognosis of HCC is variable according to different stages due to feasibility of therapeutic options.³ Radical resection of tumor is recommended for patients with a solitary tumor and preserved liver function without extrahepatic metastasis, whereas liver transplantation provides survival benefits for unresectable cases within Milan criteria (solitary tumor ≤ 5 cm or up to three nodules ≤ 3 cm).^{4,5} In addition, image-guided ablation is the most frequently applied strategy with limitations of size and localization of the tumor.⁶ For multifocal disease without vascular invasion and extrahepatic metastasis, chemoembolization has been suggested to be promising therapy for improvement of prognosis.⁷ Despite candidate selection criteria according to the disease status, recent advances revealed that diagnosis at an early stage is the optimum approach for to achieve favorable prognosis by offering curative treatment options.⁸

To date, approximately 20% of patients with HCC are diagnosed at early stage and benefit from potentially curative ablative treatments.⁹ According to a study involving 5 Dutch centers, surveillance (≥ 2 screening tests during 3 preceding years and at least once of imaging test within 18 months before development of HCC) was found to be an independent prognostic factor that predicts favorable outcomes.¹⁰ A randomized controlled trial including 18,816 patients with hepatitis B virus (HBV) infection demonstrated that surveillance by biannual α -fetoprotein test and ultrasonography examination ameliorated HCC-related mortality from 83.2/100,000 (screening group) to 131.5/100,000 (control group) with a hazard ratio (HR) of 0.63 (95% CI, 0.41 to 0.98), which indicates 37% of decrease in HCC-related mortality.¹¹

Although a validation trial is yet to be carried out, since the only opportunity to provide effective treatments with long-term survival is the detection of the tumor at an early stage, surveillance is crucial predictor for favorable prognosis.

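### Very early HCC is a stated aim without a definition, and no planned analysis measures the signature's accuracy by tumour stage

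*Combined protocol and SAP*

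**What the plan says.** The Abstract (Background) gives two joint aims for the biosignature: to stratify risk, and "to diagnosis hepatocellular carcinomas at very early stage using biological signature". The Introduction repeats this, saying the trial is designed "to conduct a signature to detect and define very early HCC and individuals at high risk of HCC". The Abstract (Methods) adds that the primary endpoints will feed three uses, one of them very early diagnosis, but gives no method.

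Outcome definitions describes the HCC endpoint as "the time from the date of inclusion to development of HCC", with no stage, tumour size or nodule number. The only size limits in the document are the Milan transplant limits, given as background in the Introduction: "solitary tumor ≤ 5 cm or up to three nodules ≤ 3 cm". The nearest stage-like outcome is the secondary endpoint LRR, a count of patients with a resectable liver malignancy free of vascular invasion and spread beyond the liver.

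Statistical analysis plans Cox and logistic screening of factors, a correlation check, and one use of ROC: "receiver operating characteristic (ROC) curves will be constructed to calculate optimum threshold for setting of cut-off value to define high risk for HCC". Sensitivity and specificity are mentioned once, in general terms. The Discussion says predictors for diagnosing very early HCC will come from comparing HCC cases with patients who do not develop HCC. Table 2 has one general row for endpoint evaluation and no staging row. Its footnote c requires contrast-enhanced CT or MRI when ultrasound shows hepatic nodules.

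**The concern.** An aim to diagnose tumours at a very early stage needs three things: a reference definition of that stage, a record of which tumours meet it, and an accuracy estimate in those tumours. The plan specifies none of them. What it does specify is a contrast that pools all stages and a cut-off for future risk.

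Later tumours may be easier to detect from blood than very early ones. If so, the pooled accuracy would look better than the accuracy in the tumours the trial is named for, and nothing in the planned output would reveal this. If the definition is left until signature scores are known, it can also be chosen to suit them.

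**Working it through.** **Plan's own figure.** No stated figure bears on this point. The sample size is 5000 + 5000 = 10,000, which adds up, but no HCC incidence, expected event count or target accuracy is given. The point therefore rests on the text, and the arithmetic below only illustrates its size.

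**Passages side by side**

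| Needed for the aim | What the document has |
|---|---|
| Definition of very early HCC | None; Milan limits as transplant background only (Introduction) |
| Stage at diagnosis | None in the HCC endpoint; no staging row in Table 2 |
| Accuracy in very early HCC | None; the ROC sets a high-risk cut-off (Statistical analysis) |
| Case-control contrast | All HCC versus no HCC (Discussion) |

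**What a pooled sensitivity can hide.** Let w be the share of tumours that are very early, a the sensitivity in those, b the sensitivity in later tumours, and P the pooled value:

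P = w × a + (1 − w) × b, so a = (P − (1 − w) × b) / w.

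Take P = 0.80 (assumed). The lowest a comes from b = 1. The highest, a = 1, is attainable in every row at the b shown.

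| w (assumed) | Lowest a | b when a = 1 | Range for a |
|---|---|---|---|
| 0.20 | (0.80 − 0.80) / 0.20 = 0 | (0.80 − 0.20) / 0.80 = 0.75 | 0-100% |
| 0.40 | (0.80 − 0.60) / 0.40 = 0.50 | (0.80 − 0.40) / 0.60 = 0.67 | 50-100% |
| 0.60 | (0.80 − 0.40) / 0.60 = 0.67 | (0.80 − 0.60) / 0.40 = 0.50 | 67-100% |

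A less extreme example: a = 0.40 and b = 0.90 at w = 0.20 give 0.2 × 0.4 + 0.8 × 0.9 = 0.80. The 20% share borrows the Abstract's background figure, "Approximately 20% patients are diagnosed to hepatocellular carcinoma at early stage", which concerns early rather than very early disease.

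**How many very early cases to expect.** The document gives no incidence, so 0.5-4% a year is assumed, with no dropout or competing death. Counts are per cohort of 5000, by month 12.

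- *Rate read as diagnoses.* 5000 × (1 − exp(−0.005)) = 25 and 5000 × (1 − exp(−0.04)) = 196 HCC. At a 20% share, 5 and 39 are very early.
- *Rate read as tumour onset.* Here ultrasound must find the tumour. Take s = 0.6, the lower end of the Introduction's figure ("Ultrasonography has a reported sensitivity of 60 to 80" percent), with independent misses and persisting tumours. Tumours starting in months 0-6 have two chances by month 12, so 1 − 0.4² = 0.84 are found; those starting in months 6-12 have one, so 0.60 are found. At 4%: 99.0 × 0.84 + 97.0 × 0.60 = 141 diagnosed, of which 20% is 28. At 0.5%: 12.5 × 0.84 + 12.5 × 0.60 = 18, of which 20% is about 4.

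Other shares scale these counts in proportion.

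**Precision.** Wilson 95% intervals for an observed sensitivity near 40%: 2/5 gives 12-77%; 16/39 gives 27-57%. With the smaller onset-based counts the intervals are wider.

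**The case against.** The strongest reply is that stage is within reach. LRR already needs vascular invasion and metastasis to be known, and footnote c to Table 2 requires CT or MRI for ultrasound nodules, so size and number could be read from reports later. That is fair, and it makes the repair cheap. But LRR covers any liver malignancy, has no size or number limit, and is not linked to signature accuracy. No variable or analysis by stage is planned.

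A second reply is that the 20% share is a weak stand-in. It is a background figure for early disease, and a cohort scanned every six months may have a larger share. This stands: the 0-100% range is the extreme of the illustration, and at 40-60% the floor is 50-67%.

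Three stronger readings should be resisted.

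- A reader might infer that the trial is incapable of assessing very early HCC. The scheduled imaging does not support that; the gap is in definition, recording and analysis.
- A reader might infer from "to conduct a signature to detect and define very early HCC and individuals at high risk of HCC" that the signature serves as its own reference standard. The same verbs also govern individuals at high risk, so the phrase may simply mean identify.
- A reader might infer that the plan fails because it does not compare the signature with ultrasound or serum tumour markers. The Abstract and Discussion offer better accuracy than current surveillance as rationale and expectation, but no endpoint or formal objective claims it, so such a comparison is not needed for this point.

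**Conclusion.** The concern holds. Very early diagnosis is a formal aim with no criterion, no staged endpoint and no accuracy analysis by stage, and the one contrast named for it pools all HCC. The plan as written cannot show whether that aim is met. This conclusion rests on the text alone.

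The size is conditional. An 80% pooled sensitivity leaves very early sensitivity anywhere in 0-100%, 50-100% or 67-100% at assumed very early shares of 20%, 40% and 60%. Nothing in the documents shows that the signature will perform poorly in very early tumours; the point is that the planned output could not tell. The risk-stratification aim is unaffected, so this is a change that should be made rather than a flaw that undoes the trial.

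**What to change.** In the SAP:

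1. Define very early HCC independently of the signature, by a size, number and vascular-invasion criterion that the sponsor sets before scores are analysed.
2. Record those items at diagnosis from the confirmatory imaging reports.
3. Report signature sensitivity separately for very early and later HCC, at the chosen cut-off and alongside its specificity in patients without HCC, with 95% CIs, per cohort. Use held-out or cross-validated scores, repeating factor screening and cut-off choice inside each fold.
4. Use the blood sample from the visit that led to diagnosis. Report the sample from one visit earlier separately, as prediction.
5. Before using visits after month 12, reconcile Blood collection for biosignature analysis (months 18-36 from high-risk patients only) with Table 2 (samples marked at all visits, without that restriction).
6. Limit any claim about very early diagnosis to what this analysis supports.

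The cost is SAP wording and a few extra data fields, on the assumption that imaging reports contain size, number and vascular invasion, which the documents do not say. The main downside is few very early cases, so the stage-specific estimates should be labelled descriptive.
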